4. SUBJECT DISPOSITION

4.1. Subject Enrollment and Disposition

A summary of subject enrollment will be provided by treatment group for each country, investigator within a country, and overall. The summary will present the number and percentage of subjects randomized. For each column, the denominator for the percentage calculation will be the total number of subjects randomized for that column.

A similar enrollment table will be provided by randomization stratum and overall. The denominator for the percentage of subjects in the stratum will be the total number of randomized subjects within each stratum. If there are discrepancies in the value used for stratification assignment between the IWRS and the clinical database, the value collected in the clinical database will be used for the summary. A listing of subjects with the IWRS randomization strata that differ from stratification factor data entered in the clinical database at the time of data finalization will be provided.

The randomization schedule used for the study will be provided as an appendix to the CSR.

A summary of subject disposition will be provided by treatment group and overall. This summary will present the number of subjects screened, the number of subjects randomized, and the number and percentage of subjects in each of the categories listed below:

- Randomized
- Full Analysis Set
- Safety Analysis Set
- Per-Protocol Analysis Set
- Completed treatment with study drug per protocol
- Did not complete study drug treatment with reasons for premature discontinuation of study drug
- Completed study
- Did not complete the study with reasons for premature discontinuation of study
- Completed Extended Viral Load Monitoring Period
- Did not complete Extended Viral Load Monitoring Period with reasons for premature discontinuation of Extended Viral Load Monitoring Period

The denominator for the percentage calculation will be the total number of subjects in the Safety Analysis Set corresponding to that column. The following by-subject listings will be provided by subject ID number in ascending order to support the above summary tables:

- Reasons for premature study drug or study discontinuation
- Reasons for screen failure (will be provided by screening ID number in ascending order)

4.2. Extent of Study Drug Exposure and Adherence

Extent of exposure to study drug will be examined by assessing the total duration of exposure to study drug and the level of adherence to the study drug specified in the protocol.

4.2.1. Duration of Exposure to Study Drug

Total duration of exposure to study drug will be defined as last dose date minus first dose date plus 1, regardless of temporary interruptions in study drug administration, and will be expressed in days (recorded to 1 decimal place, eg, 4.5 days). If the last study drug dosing date is missing, the latest study drug end date, clinical visit date, laboratory sample collection date, or vital signs assessment date that occurred during the on-treatment period will be used.

The total duration of exposure to study drug will be summarized using descriptive statistics (number of subjects [n], mean, SD, median, Q1, Q3, minimum, and maximum), and using the number and percentage of subjects exposed through the following time periods: Day 1 (Baseline), Day 5, Day 9, Day 13, and Day 17. Summaries will be provided by treatment group for the Safety Analysis Set.

Summaries will be provided by treatment group for the Safety Analysis Set. No inferential statistics will be provided

4.2.2. Adherence to Study Drug

The total number of doses administered will be summarized using descriptive statistics. Adherence is calculated based on the total amount of study drug (mg) administered and the expected amount per protocol:

$$\text{Prescribed Adherence (\%)} = \left(\frac{\text{Total Amount of Study Drug Administered}}{\text{Total Amount of Study Drug Specified by Protocol}} \right) \times 100$$

Descriptive statistics for adherence (sample size, mean, SD, median, Q1, Q3, minimum, and maximum) along with the number and percentage of subjects belonging to adherence categories (eg, < 80% and ≥ 80%) will be provided by treatment group for the Safety Analysis Set. No inferential statistics will be provided.

A by-subject listing of study drug administration and drug accountability will be provided separately by subject ID number (in ascending order) and visit (in chronological order).

4.3. Protocol Deviations

Subjects who did not meet the eligibility criteria for study entry will be summarized regardless of whether they were exempted by the sponsor or not. The summary will present the number and percentage of subjects who did not meet at least 1 entry criterion and the number of subjects who violated specific entry criteria by treatment group based on all enrolled subjects. A by-subject listing will be provided for those subjects who violated at least 1 inclusion or exclusion criterion. The listing will present the entry criterion (or criteria if more than 1 violation) that subjects did not meet and related comments, if collected.

Protocol deviations occurring after subjects entered the study are documented during routine monitoring. The number and percentage of subjects with important protocol deviations by deviation reason (eg, nonadherence to study drug, violation of inclusion/exclusion criteria) will be summarized by treatment group for all Randomization Analysis Set. A by-subject listing will be provided for those subjects with any protocol deviation.

5. BASELINE CHARACTERISTICS

5.1. Demographics

Subject demographic variables (ie, age, sex, race, and ethnicity) will be summarized by treatment group and overall using descriptive statistics for age, and using number and percentage of subjects for sex, race, and ethnicity. Age at baseline is calculated in years at the first dosing date of study drug. The summary of demographic data will be provided for the Safety Analysis Set.

In addition, a similar summary table will be provided by stratification factors (ie, presence or absence of lymphopenia and treatment of RSV infection with ribavirin [yes or no] prior to randomization).

A by-subject demographic listing, which includes the date when informed consent was signed, will be provided by subject ID number in ascending order.

5.2. Other Baseline Characteristics

Other baseline characteristics include stratification factors, body weight (in kg), height (in cm), body mass index (BMI; in kg/m²), RSV types (RSV A or RSV B), vital signs, O₂ saturation, smoking history, RSV viral load, detectable RSV in nasal samples, co-pathogen types, duration of respiratory symptoms prior to the first dosing date, hospitalization status, serum antibody titer to RSV, and FLU-PRO score. These baseline characteristics will be summarized by treatment group and overall using descriptive statistics (n, mean, SD, median, Q1, Q3, minimum, and maximum) for continuous variables and using the numbers and percentages of subjects for categorical variables. For baseline body weight, height, and BMI, descriptive statistics also will be presented by sex in the same table. In addition, baseline characteristics will be summarized by the consent status of participation in the Extended Viral Load Monitoring (yes or no) and by LRTC occurrence (subjects who did and did not develop LRTC) in a separate table, respectively. The summary of baseline characteristics will be provided for the Safety Analysis Set.

A by-subject listing of the baseline characteristics will be provided by subject ID number in ascending order.

5.3. Medical History

Medical history will be collected at screening for disease-specific and general conditions (ie, conditions not specific to the disease being studied).

HCT-specific medical history will be summarized by treatment group and overall using descriptive statistics (n, mean, SD, median, Q1, Q3, minimum, and maximum) for continuous variables and using the numbers and percentages of subjects for categorical variables. A summary of HCT-specific medical history will be provided for the Safety Analysis Set. No inferential statistics will be generated.

A by-subject listing of medical history (HCT and respiratory conditions) will be provided by subject ID number in ascending order.

General medical history will not be coded, but will be listed only.

6. EFFICACY ANALYSES

6.1. Definition of the Co-Primary Efficacy Endpoints

The co-primary efficacy endpoints of this study are: the time-weighted average change in nasal RSV viral load (\log_{10} copies/mL) from Baseline (Day 1) to Day 9 and the proportion of subjects who develop a LRTC through Day 28.

6.1.1. Time-weighted average change in nasal RSV viral load

The time-weighted average change in nasal RSV viral load (\log_{10} copies/mL) from Baseline (Day 1) to Day 9 as measured by RT-qPCR is defined as:

$$\frac{\sum_{i=a}^{b-1} \{0.5 \times (Y_i + Y_{i+1}) \times (t_{i+1} - t_i)\}}{(t_b - t_a)}$$

where Y_i is the change from Baseline in RSV \log_{10} viral load at Visit i , t is the time at the specified timepoint (the actual study day), a is the baseline assessment at Day 1, and b is the last assessment at or prior to Day 9 visit.

The time-weighted average change, often referred to as the DAVG, provides the average viral burden change from baseline.

6.1.2. Proportion of subjects who develop a LRTC through Day 28

The proportion of subjects who develop a LRTC through Day 28, defined as 1 of the below, will be adjudicated by an Endpoint Adjudication Committee (EAC).

- Primary RSV LRTI
- Secondary bacterial LRTI
- Lower respiratory tract infection due to unusual pathogens
- Lower respiratory tract complication of unknown etiology

The EAC will review related clinical data to determine whether a LRTC has developed. The EAC's role and responsibilities and the data to be provided to the EAC are described in a mutually agreed upon EAC charter. The EAC charter defines the EAC membership, adjudication process, meeting logistics, and meeting frequency.

6.2. Statistical Hypotheses for the Co-Primary Efficacy Endpoints

The co-primary analyses will test for superiority the 2 null hypotheses in the following sequence:

- H_{01} : There is no difference between presatovir and placebo in the time-weighted average change in RSV \log_{10} viral load from Day 1 to Day 9
- H_{02} : There is no difference between the presatovir and placebo treatment groups in the proportion of subjects who develop an LRTC through Day 28.

The co-primary endpoint analyses will be performed on FAS.

6.2.1. Time-Weighted Average Change in Nasal RSV Viral Load

The treatment difference in the time-weighted average change from Baseline (Day 1) to Day 9 in nasal RSV viral load (\log_{10} copies/mL) will be analyzed using a parametric ANCOVA with the baseline viral load (\log_{10} copies/mL) and stratification factors as covariates in the model. The test will be 2-sided with the significance level of 0.01. Nonparametric methods such as rank-based ANCOVA models or Wilcoxon rank sum tests may be implemented for exploratory purposes.

Adjusted means for each treatment group, 99% confidence interval (CI), and descriptive statistics (sample size, mean, SD, median, Q1, Q3, minimum, and maximum) will be presented in the descriptive summaries. Missing viral load data will be handled using the method described in Section 3.6.

6.2.2. Proportion of Subjects Who Develop a LRTC through Day 28

The proportion of subjects who develop a LRTC through Day 28 will be analyzed using a 2-sided Cochran-Mantel-Haenszel test stratified by the randomization stratification factors. The significance level used for the analysis (eg, 0.04 or 0.05) will be determined based upon the decision to reject the null hypothesis of the other co-primary endpoint as described in Section 3.5. The 2-sided 95% CI for the odds ratios between the 2 treatment groups will be constructed based on stratum-adjusted Mantel-Haenszel proportions.

The numbers and percentages of subjects who develop a LRTC through Day 28 will be provided with 95% CIs for the percentages based on the Clopper-Pearson method {Clopper 1934}.

The final analysis will be performed when all randomized subjects either complete Day 28 assessments or discontinue study prematurely.

The analyses of the co-primary endpoints will be repeated using the PP analysis set.

The primary efficacy analyses will also be repeated for the subgroups specified in Section 3.4, including the stratification factors (presence or absence of lymphopenia, treatment of RSV infection with ribavirin [yes or no] prior to randomization, sex, race, age group [< 65 or ≥ 65], type of transplant [autologous HCT or allogeneic HCT]. Adjusted mean and 95% CI will be presented by treatment group for exploratory purposes.

In addition, the effect of various baseline characteristics on the primary outcomes, including the type of transplant, will be explored using regression models with the baseline characteristics included as effects in the model for a sensitivity analysis.

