1.4. Dose Rationale

The dose and administration schedule selected for this study is a single dose of 200 mg presatovir administered orally or via NG tube on Days 1, 5, 9, 13, and 17. This regimen was selected based upon the PK characteristics of presatovir and the pharmacokinetic/pharmacodynamic (PK/PD) relationship established in the antiviral effect study with different doses/regimens in Study GS-US-218-0103.

In Study GS-US-218-0103, a 5-day treatment regimen of presatovir (50 mg single dose on Dose Day 1, followed by 25 mg once daily on Dose Days 2 through 5) resulted in a significant reduction in RSV viral load. The mean AUC of RSV viral load as measured by the RT-qPCR assay from first viral load measurement post initial dose of study drug through end of quarantine (Day 12) was significantly lower in presatovir subjects compared to placebo subjects ($\Delta = 506.9 \log_{10} \text{PFUe} \cdot \text{hour/mL}$, $p < 0.001$). This 5-day regimen was able to achieve presatovir trough concentrations ~4-5 fold of paEC_{95} (52 ng/mL) for up to 120 hours following dose initiation for the virus used in the challenge study, the M37 strain of RSV.

In selecting the dose for the current study, the goal was to achieve presatovir trough concentrations above 4-fold of paEC_{95} for 95% of of the clinical RSV isolates for the duration of RSV shedding in HCT patients. Longitudinal viral dynamics data from investigators at an academic HCT center also indicate that the majority of HCT patients shed RSV for 15 days, but some may shed for as long as 21 days (unpublished). In addition, recent studies indicate that the mean time to progression of URTI to LRTI is 7 days, with 90% of subjects progressing within 15 days after presenting with a URTI {[Shah et al 2013](#)}, {[Kim et al 2014](#)}. Therefore, a total of 5 doses of presatovir (200 mg each dose, every 4 days) is expected to provide > 4-fold paEC_{95} coverage for ~95% of 75 wild-type clinical RSV isolates through Day 22, which is expected to result in significant durable antiviral effect.

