4.2. Inclusion Criteria

Subjects must meet all of the following inclusion criteria to be eligible for participation in this study.

- 1) Adult male and female subjects 18 to 75 years of age. In Japan subjects must be 20 to 75 years of age. In Singapore subjects must be 21 to 75 years of age.
- 2) Received an autologous or allogeneic HCT using any conditioning regimen
- 3) Documented to be RSV-positive as determined by local testing (eg, PCR, DFA, RVP assay, or culture) using an upper respiratory tract sample collected ≤ 6 days prior to Day 1, or as determined at Screening as per Section 6.1.1
- 4) New onset of at least 1 of the following respiratory symptoms for ≤ 7 days prior to Day 1: nasal congestion, runny nose, cough, or sore throat, or worsening of one of these chronic (associated with a previously existing diagnosis, eg, chronic rhinorrhea, seasonal allergies, chronic lung disease) respiratory symptoms ≤ 7 days prior to Day 1
- 5) No evidence of new abnormalities consistent with LRTI on a chest X-ray relative to the most recent chest X-ray, as determined by the local radiologist. If a chest X-ray is not available or was not obtained during standard care < 48 hours prior to Screening, a chest X-ray must be obtained for Screening
- 6) O_2 saturation $\geq 92\%$ on room air
- 7) An informed consent document signed and dated by the subject or a legal guardian of the subject and the investigator or his/her designee. In Sweden ICFs signed by a legal guardian must also be signed by a close relative of the subject.
- 8) A negative urine or serum pregnancy test is required for female subjects (unless surgically sterile or greater than two years post-menopausal)
- 9) Male and female subjects of childbearing potential must agree to contraceptive requirements as described in [Appendix 5](#)
- 10) Willingness to complete necessary study procedures and have available a working telephone or email

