15.9.1.1.10	Time-Weighted Average Change in Nasal RSV Viral Load (log ₁₀ copies/mL) from Baseline to Day 9 by RSV Type	Full Analysis Set
15.9.1.1.11	Time-Weighted Average Change in Nasal RSV Viral Load (log ₁₀ copies/ml) from Baseline to Day 9 by Duration of RSV Symptoms at Baseline	Full Analysis Set
15.9.1.1.12	Time-Weighted Average Change in Nasal RSV Viral Load (log ₁₀ copies/ml) from Baseline to Day 9 by Baseline Viral Load Values	Full Analysis Set
15.9.1.2.1	Proportion of Subjects with Progression to Lower Respiratory Tract Infections through Day 28	Full Analysis Set
15.9.1.2.2	Proportion of Subjects with Progression to Lower Respiratory Tract Infections through Day 28	Per Protocol Analysis Set
15.9.1.2.3	Proportion of Subjects with Progression to Lower Respiratory Tract Infections through Day 28	Full Analysis Set (Sensitivity Analysis)
15.9.1.2.4	Proportion of Subjects with Progression to Lower Respiratory Tract Infections through Day 28 by Presence or Absence of Lymphopenia	Full Analysis Set
15.9.1.2.5	Proportion of Subjects with Progression to Lower Respiratory Tract Infections through Day 28 by Actual Ribavirin Use at Baseline	Full Analysis Set
15.9.1.2.6	Proportion of Subjects with Progression to Lower Respiratory Tract Infections through Day 28 by Type of Transplant	Full Analysis Set
15.9.1.2.7	Proportion of Subjects with Progression to Lower Respiratory Tract Infections through Day 28 by Age	Full Analysis Set
15.9.1.2.8	Proportion of Subjects with Progression to Lower Respiratory Tract Infections through Day 28 by Sex	Full Analysis Set
15.9.1.2.9	Proportion of Subjects with Progression to Lower Respiratory Tract Infections through Day 28 by Race	Full Analysis Set
15.9.2.1.1	Proportion of Subjects Developing Respiratory Failure Requiring Mechanical Ventilation or All-Cause Mortality Through Day 28	Full Analysis Set
15.9.2.1.2	Proportion of Subjects Developing Respiratory Failure Requiring Mechanical Ventilation or All-Cause Mortality Through Day 28	Per Protocol Analysis Set
15.9.2.1.3	Proportion of Subjects Developing Respiratory Failure Requiring Mechanical Ventilation or All-Cause Mortality Through Day 28 by Presence or Absence of Lymphopenia	Full Analysis Set

Table Number	Title	Analysis Set
15.9.2.1.4	Proportion of Subjects Developing Respiratory Failure Requiring Mechanical Ventilation or All-Cause Mortality Through Day 28 by Actual Ribavirin Use at Baseline	Full Analysis Set

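### Symptom duration at first dose is collected and used to tabulate viral load, but it is left out of the primary viral-load model and not named in the sensitivity regressions: a modest, avoidable loss of precision

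*SAP*

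**What the plan says.** Protocol 4.2, criterion 4, admits subjects with "New onset of at least 1 of the following respiratory symptoms for ≤ 7 days prior to Day 1", or with worsening of a chronic respiratory symptom over the same period.

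SAP 5.2 lists "duration of respiratory symptoms prior to the first dosing date" among the baseline characteristics. SAP 12.1 plans Table 15.9.1.1.11, the DAVG "from Baseline to Day 9 by Duration of RSV Symptoms at Baseline". Table 15.9.3.1.4 and Figures 15.9.1.3 and 15.9.1.4 show viral load by visit, split the same way.

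The primary DAVG model in SAP 6.2.1, as in Protocol 8.5.1, takes baseline viral load "and stratification factors as covariates in the model. The test will be 2-sided with the significance level of 0.01". The strata are lymphopenia and ribavirin treatment. The LRTC comparison in SAP 6.2.2 is a "2-sided Cochran-Mantel-Haenszel test stratified by the randomization stratification factors".

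SAP 3.4 does not name symptom duration as a subgroup. The LRTC subgroup tables run from 15.9.1.2.4 to 15.9.1.2.9, the last being "Proportion of Subjects with Progression to Lower Respiratory Tract Infections through Day 28 by Race". Table 15.8.3.2.3 summarizes baseline characteristics by LRTC occurrence. The paragraph that closes SAP 6.2.2 plans regressions of the primary outcomes on baseline characteristics as a sensitivity analysis, and names only type of transplant.

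**The concern.** The DAVG runs from Day 1 to Day 9 after first dose, so it covers a different stretch of the illness in a subject who enters on symptom day 1 than in one who enters on day 7. Baseline viral load does not fully identify the stage, because the same value may be on the way up or on the way down. Duration is therefore a plausible predictor of the DAVG beyond the covariates already in the model, and the sponsor treats it as relevant enough to tabulate and plot viral load by it.

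Two things are at stake. Any variation that duration explains stays in the error term of a test at two-sided 0.01, and a chance difference between arms in illness stage is not adjusted for. In addition, because the sensitivity regressions leave most of their covariates unnamed, whether duration enters them could be settled after the treatment codes are known.

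**Working it through.** **Inputs.** SAP 1.3: difference 1 log10, SD 2, two-sided alpha 0.01, 100 per arm, power stated as over 80%; LRTC 30% on placebo, a 20% reduction, alpha 0.04, power stated as over 90%; 189 subjects enrolled at the halt. Allocation is 1:1, so 95 and 94 is assumed. R², the share of residual DAVG variance that duration explains, is assumed; the documents give none.

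**1. The plan's own figures.**
- DAVG: noncentrality = difference / (SD × √(1/n1 + 1/n2)) = 1 / (2 × √(2/100)) = 3.536. The critical t on 198 degrees of freedom is 2.601, and power is 82.4% (normal approximation 83.1%). The stated figure holds.
- LRTC: 30% against 10% gives 93.7% (Fisher's exact test 92.1%). The stated figure holds with the reduction read as 20 percentage points.

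**2. DAVG at 189 subjects, with and without duration.** √(1/95 + 1/94) = 0.1455. The residual SD is 2 × √(1 − R²).

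| Assumed R² | Residual SD | Noncentrality | Power |
|---|---|---|---|
| 0 (planned model) | 2.000 | 3.437 | 79.7% |
| 0.03 | 1.970 | 3.490 | 81.1% |
| 0.10 | 1.897 | 3.623 | 84.5% |

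The critical t is 2.602 on 187 degrees of freedom. Giving up one more degree of freedom for the covariate does not change the first decimal. In sample-size terms, 1/(1 − R²) is 1.03 to 1.11, or 3 to 11% more subjects. All of this is before subjects without a quantifiable baseline viral load leave the FAS.

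**3. Chance imbalance.** If duration is spread evenly over days 0 to 7 (assumption), its SD is 2.29 days. With 100 per arm, the 95% range of the difference in mean duration is ±1.96 × 2.29 × √(2/100) = ±0.64 day. With an assumed slope of 0.1 to 0.3 log10 per day, the estimated treatment difference shifts by 0.06 to 0.19 log10, against a design difference of 1.

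**4. LRTC.** A simulation of the CMH test (100 per arm, 30% against 10%, alpha 0.04, log-odds slope on duration 0 to 0.3 per day, 4,000 runs per setting) gave power of 94.1 to 94.6% without duration and 94.5 to 95.2% with a stratum for 0–3 against 4–7 days. The largest gain in any setting was about 1 point. Type I error was 3.6 to 4.2% and 3.8 to 4.2%, against a nominal 4%.

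**5. What an LRTC table by duration could show.** With 94.5 per arm, two equal duration groups and 30% LRTC in both arms (assumption), the 95% interval for each within-group difference is ±1.96 × √(2 × 0.3 × 0.7 / 47.25) = ±18.5 points.

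**The case against.** The strongest reply is that nothing here is an error. Baseline value plus randomization strata is a standard prespecified model, it matches the protocol, and leaving out a further covariate does not bias a randomized comparison. That stands.

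The assumed gain can also be questioned. SAP 1.3 gives SD 2 for the DAVG itself, not for the residual after the planned covariates. If those already explain 20% (assumption), the residual SD is 2 × √0.8 = 1.79, and the same formula gives 89.1% at 189 subjects, rising to 90.2 to 92.5%. The gain is then smaller, though still positive. Duration is also an imperfect clock, since for chronic symptoms entry is dated from worsening.

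The change has a procedural cost too. SAP 2.2 reports two interim efficacy analyses, with unblinded results going to sponsor executives. Altering a protocol-specified model at that point invites questions even though the study team is blinded. This stands as a reason to document the change and keep the current model alongside it.

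A reader might infer three stronger points that the documents do not support:

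- **That the LRTC analysis ignores duration altogether.** Table 15.8.3.2.3 covers it descriptively. What is absent is a comparison of the arms within duration groups.
- **That a subject entering on day 7 is already past the mean time to progression.** Protocol 1.4 says "the mean time to progression of URTI to LRTI is 7 days, with 90% of subjects progressing within 15 days after presenting with a URTI". That clock starts at presentation, which the documents do not equate with symptom onset.
- **That LRTC risk falls steeply across the entry window.** Such a calculation needs the 30% placebo rate to be the risk at symptom day 0, but SAP 1.3 gives it for enrolled placebo subjects. Putting it at day 0 with an exponential mean of 7 days, risk on day d = 0.3e^(−d/7) / (0.7 + 0.3e^(−d/7)), gives an average of 21% over an even 0-to-7-day entry, which contradicts the 30%.

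**Conclusion.** The point holds as a missed gain in precision, not as a flaw in the primary analysis. Both planned tests are valid under randomization, and type I error is not affected. Duration is collected and already used descriptively for viral load, but it is absent from the DAVG model and unnamed in the sensitivity regressions.

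On an assumed residual R² of 0.03 to 0.10, adding it raises DAVG power at 189 subjects by 1.4 to 4.8 points. At SD 2 that would bring power back above the planned 80%, before FAS exclusions. The size rests wholly on that R² and on SD 2 being the residual SD. For LRTC the effect on power is about 1 point or less.

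It may be tempting to say that an LRTC table by duration would separate late treatment from lack of effect. With intervals of about ±18.5 points per half, it would not.

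**What to change.** Before the study team is unblinded:

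1. In SAP 6.2.1, add symptom duration at first dose (days, continuous) to the DAVG ANCOVA. State how days are counted for subjects who enter on worsening of a chronic symptom. Record this as a change from Protocol 8.5.1, and keep the current model as a sensitivity analysis.
2. In the closing paragraph of SAP 6.2.2, name symptom duration as a fixed term in the regressions for both co-primary endpoints.
3. Optionally, add to SAP 12.1 an LRTC-by-treatment table using the categories of Table 15.9.1.1.11, labelled descriptive. The legible text gives no cut-points for those categories, so they should be stated.

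The cost is one degree of freedom, some SAP wording and perhaps one table, with no new data. The real price is a documented change to the primary model after two interim looks. The blinded study team should therefore make it without input from anyone who saw those results, and the SAP should say so. If the sponsor will not alter the primary model at this stage, item 2 alone still fixes the covariate before unblinding.
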